10.2 SECONDARY EFFICACY MEASURES

The secondary endpoints are as follows:

- Change in OI from Baseline to Hours 12, 24, and 72, and Days 7 and 14 and/or prior to study drug discontinuation/weaning
- Change in PaO₂/FiO₂ (P/F ratio) from Baseline to Hours 12, 24, and 72
- Change in pre- and post-ductal SpO₂ from Baseline to Hours 6, 12, 24, and 72
- Time to discontinuation of iNO
- Time on mechanical ventilation
- Time to initiation of ECMO
- Time to clinical worsening
- Change in NT-proBNP

10.2.2 Change in PaO₂/FiO₂

PaO₂/FiO₂ and change from Baseline in PaO₂/FiO₂ will be analyzed in a similar manner as described in Section 10.2.1 at 12 hours, 24 hours, and 72 hours.

10.2.3 Change in SpO₂

Pre- and post-ductal SpO₂ and change from Baseline in pre- and post-ductal SpO₂ will each be analyzed in a similar manner as described in Section 10.2.1. Additionally, change from Baseline in pre- and post-ductal SpO₂ will be summarized by treatment group at 6 hours, 12 hours, 24 hours, and 72 hours.

10.2.4 Change in NT-proBNP

NT-proBNP and change from Baseline in NT-proBNP at Day 14 will be analyzed as described in Section 10.2.1 at Day 7 and Day 14. The listing will include normal range and high/low flags as well as all collected assessments of NT-proBNP.

10.2.5 Time to Clinical Worsening

Data on the clinical worsening assessment page of the eCRF will be used to determine clinical worsening status. Clinical worsening events including the date (study day) of the event and details of the clinical worsening event will be listed. The time to clinical worsening will be calculated according to the rules specified in [Table 8-1](#).

Time to clinical worsening will be summarized by treatment group using product-limit estimates calculated by the Kaplan-Meier method, and displayed graphically as Kaplan-Meier curves. A tabular summary of this analysis will include the number of subjects at risk (sample size), estimated median duration, and a 95% confidence interval for the median duration for each treatment group. The log-rank test will be used to calculate the p-value for treatment differences.

The SAS Procedure LIFETEST will be used. The pseudo SAS statements are listed below:

```
proc lifetest;
  time TimeToWorsening*Censor_Status(1);
  strata Treatment;
run;
```

In addition, the Cox proportional hazards model will be fit to obtain the hazard ratio. The model will include treatment as an explanatory variable. The SAS procedure PHREG will be used.

The pseudo SAS statements are listed below:

```
proc phreg;
  Model TimeToWorsening*Censor_Status(1) = treatment
    / risklimits alpha=0.05 ties=efron;
run;
```

10.2.6 Time to Initiation of ECMO

Time to initiation of ECMO will be analyzed as described in Section 10.2.5.

10.2.7 Time to Discontinuation of iNO

Time to discontinuation of iNO will be analyzed as described in Section 10.2.5.

10.2.8 Time on Mechanical Ventilation

A listing that includes start date and time, stop date and time, and total time on mechanical ventilation will be prepared. Time on mechanical ventilation will be summarized by treatment group, as appropriate. A Wilcoxon rank sum test will be conducted to assess differences between treatment groups.

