4.2 EXCLUSION CRITERIA

A subject is ineligible for participation if any of the following criteria are met:

1. Previous or concurrent use of a PDE-5i, ERA or prostanoid. Previous receipt of prostaglandin E1 for ductal patency is allowed.
2. Significant congenital heart disease (CHD) as detected by ECHO (excluding presence of minor defects such as small secundum ASD, minor valvular abnormalities, or expected transitional findings such as a PFO, or PDA. Subjects with small muscular, restrictive VSD may be enrolled).
3. Clinically significant, untreated active pneumothorax at Screening.
4. Evidence of clinically significant bleeding (e.g., hemodynamic instability or requiring transfusion) at Screening. Note: history of a transfusion is not necessarily an exclusion criterion.
5. Necrotizing enterocolitis; defined as Bells stage II or greater at Screening.
6. Uncontrolled hypotension; defined as mean systemic pressures less than or equal to 35mmHg at Screening.

7. Uncontrolled coagulopathy and/or untreated thrombocytopenia; defined as <50,000 platelets / μ L at Screening.
8. History of severe (Grade 3 or 4) intracranial hemorrhage at Screening. Note: a cranial ultrasonography is not required during Screening.
9. Currently receiving ECMO or has immediate plans to initiate ECMO.
10. Expected duration on mechanical ventilation of less than 48 hours.
11. Life expectancy is less than two months or has a lethal chromosomal anomaly.
12. Contraindication to ECMO.
13. Bilateral congenital diaphragmatic hernia.
14. Active seizures at Screening.
15. Currently participating in another clinical drug study (excluding observational registries).

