Subjects may continue on study drug for up to 28 days if clinically indicated. Per the investigator's discretion, if the subject is treated with Remodulin beyond Day 28, Day 28 will be considered as the last day of study drug administration. These subjects will continue to be followed in the study until they have reached Day 56 (4 weeks after last dose of study drug) or have been discharged from the hospital, whichever comes first.

6.1.4 *Dose Weaning*

Abrupt cessation of study drug will be avoided due to the risk of rebound pulmonary hypertension. Inhaled NO should be weaned and discontinued prior to initiating weaning of study drug. When the subject has reached the treatment goal and is ready to start weaning, the dose of study drug will be held constant at the same dose for at least 12 hours prior to initiating down titration. It is recommended the dose of study drug be decreased by no more than 10ng/kg/min per day either in the same incremental manner as the dose was increased or as determined by the Investigator. Dose decreases in increments greater than 5ng/kg/min are recommended to be avoided, but faster weaning may occur if required per subject care.

If withdrawal from study drug is warranted, the dose of study drug will be weaned until discontinued.

6.1.5 *Initiation of ECMO*

Subjects randomized to study drug may continue to receive study drug during ECMO at the pre-ECMO dose. Subjects should not be unblinded upon initiation of ECMO, unless required for purposes of medically managing the subject. At the conclusion of ECMO, weaning of study drug can begin per the Investigator's discretion.

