10.3.2 Secondary Endpoints

Secondary endpoints (change in OI, P/F ratio, and pre- and post-ductal SpO₂, time on mechanical ventilation, and change in NT-proBNP) will be summarized and tested using group t-test. Kaplan-Meier estimate will be provided for time to event variables (time to discontinuation of iNO, time to initiation of ECMO, and time to clinical worsening) and log-rank test will be used to test the treatment differences.

Plasma samples will be analyzed for treprostinil using a validated bioanalytical plasma assay. Individual and mean treprostinil plasma concentration data, and treprostinil pharmacokinetic parameters, determined as able, will be summarized using descriptive statistics.

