- DRUG INTERRUPTED - the dose or regimen of the test agent was altered or administration of the test agent was stopped temporarily
- DRUG WITHDRAWN- administration of the test agent was stopped permanently and not restarted. This does not apply if the subject was on drug at the time of death. For this scenario “Dose not changed” would be marked.
- Not Applicable- (i.e., AE occurred prior to administration of test agent)

* Only the last action should be recorded on the CRF.

Outcome

- Fatal – The study subject died
- Not Recovered/Not Resolved – The AE was ongoing at the end of the study/AE observation period
- Recovered/Resolved – The AE resolved
- Recovered/Resolved with Sequelae – The AE is considered resolved; however, there is a residual sequelae
- Recovering/Resolving – The AE is improving but is not yet completely recovered/resolved at the end of study/AE observation period
- Unknown – The outcome of the AE cannot be determined

AE/SAE Start Date verses Serious Date

The AE start date is classified as the first day the subject experiences sign and symptoms of an event and should be entered on the eCRF and SAE Notification Form section “Onset date of symptoms.” The date the event became serious is the first day the event meet one of the serious criterion (see section 9.1.2). The start date and date event became serious could be the same date (e.g., clavicle fracture from a fall).

Note: The start date (onset) should never be a date prior to the subject signing the informed consent.

AE/SAE Stop Date

For AEs and SAEs the dates listed on the eCRF and SAE Notification Form will always be the same. For non-fatal events, this is the date the last sign and/or symptom resolved. For fatal events this is the date of Death. If the event Recovered/Resolved with Sequelae enter the date the subject's medical condition resolved or stabilized.

For SAEs follow-up must continue until resolution, death, end of study, or subject is lost to follow-up.

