8.4 MULTIPLE COMPARISONS AND MULTIPLICITY

The primary efficacy endpoint of clinical worsening through Day 14 will be tested at alpha level 0.05. If the primary efficacy endpoint is statistically significant at alpha level 0.05, the statistical tests for secondary efficacy endpoints will be performed. As these comparisons are exploratory, no adjustments for multiplicity are planned.

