8.5.3 Time to Event and Censor Status

Time to event and censor status will be calculated based on the rules in Table 8-1 for time to clinical worsening, time to initiation of ECMO, and time to discontinuation of iNO.

Table 8-1 Time to Event and Censor Status Rules

Parameter	Scenario	Formula	Censor Status
Time to Clinical Worsening (days)	Subject with clinical worsening or subject died between Baseline and Day 14	= minimum of (Worsening date, death date) - Randomization date	0 (event)
	Subject without clinical worsening between Baseline and Day 14	= minimum of (Last assessment date - Randomization date, 14)	1 (censored)
Time to initiation of ECMO (days)	Subject initiated ECMO between Baseline and Day 14	= Initiation date - Randomization date	0 (event)
	Subject did not initiate ECMO between Baseline and Day 14	= minimum of (Last assessment date - Randomization date, 14)	1 (censored)
Time to discontinuation of iNO (days)	Subject discontinued iNO between Baseline and Day 14	= iNO discontinuation date - Randomization date	0 (event)
	Subject did not discontinue iNO between Baseline and Day 14	= minimum of (Last assessment date - Randomization date, 14)	1 (censored)

ECMO, extracorporeal mechanical oxygenation; iNO, inhaled nitric oxide

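### Total ventilation time is tested with no rule for death and no stated time origin; if the time ends at death, an early death ranks as a favourable result

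*SAP*

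**What the plan says.** - SAP 10.2.8 takes total ventilation time from recorded start and stop dates and times. The only test is this: "A Wilcoxon rank sum test will be conducted to assess differences between treatment groups". No window, time origin or rule for death is given.
- Protocol 10.3.2 plans a different test for the same quantity, also with no death rule: "time on mechanical ventilation, and change in NT-proBNP) will be summarized and tested using group t-test".
- No other section fills the gap. Table 8-1 (SAP 8.5.3) gives event and censoring rules for clinical worsening, ECMO and iNO, but not for ventilation. The LOCF rule in SAP 8.3.2 does not address a duration cut short by death. Protocol 10.6 has subjects contribute data up to the point they leave, without imputation.
- Within Table 8-1, the clinical-worsening row names death ("Subject with clinical worsening or subject died between Baseline and Day 14"). The iNO row does not ("Subject discontinued iNO between Baseline and Day 14").
- SAP 8.4 limits the reach of all this: "If the primary efficacy endpoint is statistically significant at alpha level 0.05, the statistical tests for secondary efficacy endpoints will be performed". It calls these comparisons exploratory and makes no multiplicity adjustment.

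**The concern.** Every infant is ventilated at entry (Protocol 4.1), and death is part of the primary endpoint. Short ventilation is meant to be good. If the total stops at death, an infant who dies ventilated on Day 2 contributes about two days and outranks nearly every survivor.

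The test then mixes two effects that pull in opposite directions. Fewer early deaths on Remodulin would push its ventilation times up, and more early deaths would push them down. The trial could report a positive primary beside a ventilation result that contradicts it, or one that lends false support. Left unwritten, the handling of death would be settled during programming.

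**Working it through.** **1. The plan's own figure.** The documents give no figure for ventilation time, only the primary sample size (60% vs 30%, one-sided 0.05, 80% power). With mean rate 0.45:

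n = [1.645·√(2·0.45·0.55) + 0.842·√(0.6·0.4 + 0.3·0.7)]² / 0.30² = (1.157 + 0.565)² / 0.09 ≈ 33 per arm.

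This reproduces 66 in total. It supplies the arm size used below and says nothing else about ventilation.

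**2. A hand check of the mechanism.** Let d_P and d_R be the death proportions. Assume survivors' ventilation is the same in both arms and every death ranks below every survivor. Then

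P(Remodulin time > placebo time) = ½ + (d_P − d_R)/2.

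The null standard error of this quantity is √[(33+33+1)/(12·33·33)] = √(67/13,068) = 0.0716. At 20/10 percent deaths the shift is 0.05, so the mean Z is 0.05/0.0716 = 0.70. The chance that Z exceeds 1.96 is the upper tail beyond 1.26, or 10.4%. The other rows of the table follow in the same way. This is an approximate ceiling, because in practice some survivors come off the ventilator before some of the deaths occur.

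**3. Simulation.** The inputs are assumptions: lognormal ventilation from randomization in both arms (median 12 days, log-SD 0.6), deaths uniform over the stated days, and total time equal to the shorter of duration and death time. The only document figures available to set rates are mortality of 4-33% (Protocol 1.1) and 57.9% death or ECMO in a control group (SAP 5). Entries are the percentage of trials significantly against Remodulin (nominal 2.5).

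| Deaths %, placebo/Remodulin | Step 2 | Days 1-7 | Days 1-14 | Days 1-28 | Days 1-7, ventilated deaths dropped |
|---|---|---|---|---|---|
| 4/2 | 3.4 | 3 | 3 | 2.9 | 2.5 |
| 10/5 | 5.4 | 5 | 4 | 3.0 | 2.7 |
| 20/10 | 10.4 | 9 | 6 | 3.8 | 2.8 |
| 33/16.5 | 21.0 | 17 | 10 | 5.2 | 3.0 |
| 30/10 (threefold cut) | 28.7 | 24 | 13 | 6.3 | 3.2 |

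- Among trials that pass the primary gate, the days 1-7 column becomes 3, 5, 10, 21 and 28.
- The protocol's t-test gives 3, 4, 6, 12 and 15 for days 1-7.
- At 20/10, medians of 8-16 days and log-SDs of 0.4-0.9 give 6-10% for days 1-7.
- If 0-14 days of ventilation before randomization also count, 33/16.5 falls from 17% to 11.5% and 30/10 from 24% to 16%. Adding only 0-3 days changes little.
- If ECMO lengthens ventilation the effect can vanish. Deaths 15/7.5 with ECMO 45/22.5 give 7% with no lengthening and 3% at 1.25 times. At 1.5 times the result is 2% against and 3% in favour.
- The bias runs both ways. With deaths 30% on Remodulin and 10% on placebo over days 1-7 (median ventilation 7-14 days, log-SD 0.7), the raw test significantly favours Remodulin in 16-24% of trials.

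**4. The worst-rank rule.** Ranking deaths last reverses the sign in step 2, so the same arithmetic gives 5.4, 10.4, 21.0 and 28.7% in favour of Remodulin at 10/5, 20/10, 33/16.5 and 30/10. Simulation gives 5, 10, 21 and 29. Ventilator-free days give 5, 10, 19 and 26.

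**5. The iNO row.** Assume equal weaning in both arms (hazard 0.15 per day) and death or ECMO in 45/22.5 percent, falling within 3, 7 or 14 days. If every such stop is recorded as a discontinuation, the log-rank test goes against Remodulin in 16, 11 or 7% of trials. If half are recorded, the figures are 8, 6 and 4.5%. If none are recorded and the infants are censored, it is about 3% throughout.

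**The case against.** **The bias depends on data entry.** A reader might infer that the plan definitely scores an early death as a success. The documents do not support that. SAP 10.2.8 does not say what stop time is entered for an infant who dies ventilated, and if none is entered and the infant drops out, the test is near nominal. This stands, so the point must be put conditionally.

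**The time origin is open.** Infants may be up to 14 days old at screening. If earlier ventilation counts, a death on study Day 2 need not give one of the shortest totals. This also stands, and it is a second thing to define.

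**The large figures need early deaths and high mortality.** The plan assumes that a composite is halved, not that mortality falls threefold, so 24% is not a fair headline. Protocol 4.2 also excludes infants on this ground: "Life expectancy is less than two months or has a lethal chromosomal anomaly". It excludes those with a contraindication to ECMO as well, so rescue is open to all. This argument limits the size but does not remove the gap.

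**iNO.** A reader might infer that the iNO endpoint rewards death in the same way. That holds only if a stop at death or ECMO is recorded as a discontinuation, and the documents do not show that convention. Two texts lean the other way. Protocol 6.1.4 treats stopping iNO as the end of a wean: "Inhaled NO should be weaned and discontinued prior to initiating weaning of study drug". Protocol 15.1, defining withdrawal of study drug only, says: "This does not apply if the subject was on drug at the time of death". Neither is a rule for this endpoint.

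**The stakes are low and the remedy has its own shift.** The endpoint is gated and exploratory, and deaths, ventilation and iNO are listed by subject, so a careful reader could trace the cause. Both points are fair. But the gate means these tests appear exactly when the primary is positive, and the planned test itself would not show the problem.

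**Conclusion.** The point holds in conditional form. The ventilation endpoint is undefined at death and has no time origin. Under one natural reading, that time ends at death, the planned test can point the wrong way.

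The size is modest at low mortality and material only when many deaths fall early. With mortality halved and time counted from randomization, it ranges from about 3% to 17% against a nominal 2.5% for deaths in days 1-7, and from 3% to 5% for deaths over days 1-28. These figures rest on assumed death rates, death timing and ventilation lengths, and on survivors' ventilation being equal in both arms.

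A reader might also infer a threat to the main result. There is none: the primary endpoint, time to clinical worsening, alpha and sample size are untouched. The change is worth making before unblinding because it is cheap and removes a choice that would otherwise be made without a rule. The iNO row is a secondary clarification.

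**What to change.** **SAP 10.2.8.** Count ventilation from randomization. Then either keep the planned Wilcoxon test with death given the worst rank, or test ventilator-free days to Day 28 with death scored 0. State one rule for an infant withdrawn, or discharged while still ventilated. Label the endpoint a composite that includes death, and report total ventilation time and deaths by arm descriptively beside it. State that this replaces the t-test in Protocol 10.3.2.

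**SAP Table 8-1, iNO row.** State that a stop at death or ECMO is not a discontinuation event. Explicit censoring there keeps the test near nominal, though it assumes the censoring is non-informative.

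**Cost.** SAP wording and programming only. Ventilation time, iNO time and ECMO start are already recorded (Protocol Synopsis, Follow-up), and so are deaths. Follow-up to 4 weeks after the last dose reaches Day 28 unless the infant is discharged or withdrawn.

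**Downside.** The composite partly repeats the primary effect. With no effect on survivors' ventilation, it favours Remodulin in about 10% of trials at 20/10 deaths, a shift about as large as the one removed and in the opposite direction. That is why the label and the descriptive tables are part of the fix.

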11 HEALTH OUTCOMES

No health outcome assessments will be collected in this study.

12 SAFETY ANALYSES

All safety analyses will be performed on the Safety population.

12.1 EXTENT OF EXPOSURE

A listing of study drug dosing will include route of administration (IV or subcutaneous); initial dose and date and time of initial dose; and dose, date, and time of each dose change. Overall

duration of exposure will be included as well as the final dose and the maximum study drug dose reached for each subject. Summaries of initial dose, final dose, and maximum dose will be provided by treatment group. If the data warrant, these summaries will also be produced by route of administration.

12.2 ADVERSE EVENTS

All AEs will be coded to PT and SOC using the latest version of the MedDRA coding dictionary. Treatment-emergent adverse events (TEAEs) are those AEs with onset date equal to or after the start date of the study drug. TEAEs will appear in listings and summaries. Non-treatment-emergent AEs (the AEs occurring after signing the Informed Consent Form (ICF), but before receiving study drug) will be listed, but will not be included in summary tables.

The AE listings will include the AE verbatim term and its corresponding PT and SOC, all eCRF details, and a treatment-emergent indicator flag. The following AE listings will be provided:

- All AEs
- Deaths
- SAEs
- AEs leading to permanent discontinuation of study drug

All AE summaries will be sorted by overall frequency and/or SOC and will include the number and percentage of subjects experiencing each type of AE, the total number of each type of AE, and the AE rate of each type of AE. AE rate will be calculated as the total number of AEs divided by the total patient days of exposure to study drug per treatment group.

The following AE summaries will be provided:

- AEs by SOC and PT
- AEs by PT
- Deaths
- SAEs by SOC and PT
- Non-serious AEs by SOC and PT
- AEs probably or possibly related to study drug by SOC and PT
- AEs leading to permanent discontinuation by PT
- AEs by SOC, PT, and severity (mild, moderate, severe)

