3.3.2.4 Adverse Events (AEs)

Documentation of AEs will be recorded in the eCRF from the time informed consent is provided until time of screen failure, time subject is withdrawn from study, time of hospital discharge, death, or until 4 weeks after the last dose of study drug, whichever comes first. All AEs should be followed until either resolution (or return to normal or Baseline values), until judged by the Investigator to no longer be clinically significant or until 4 weeks after last dose of study drug. Subjects with ongoing AEs at the time of hospital discharge will continue to be followed for their AEs until either resolution (or return to normal or Baseline values), until judged by the Investigator to no longer be clinically significant, or until 4 weeks after last dose of study drug. All SAEs will be followed until resolution, death, or the subject is lost to follow-up, even if they are ongoing more than 4 weeks after the last dose of study drug. Sections [9](#) and [15.1](#) provide the definitions and guidelines for recording AEs. If the subject receives Remodulin after hospital discharge, beyond Day 56/End of study, or following withdrawal from the study, AEs/SAEs will be subject to AE/SAE reporting under local government post-marketing AE/SAE reporting requirements.

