7.2 BASELINE

Once all Screening activities have taken place, the following Baseline activities will occur. Once Baseline assessments have been completed and eligibility confirmed, subjects may be randomized in the IWRS. Study drug should be initiated as soon as possible after randomization.

- Physical examination (including length and weight)*
- Vital signs (BP, HR, Temp, pre- and post-ductal SpO₂)*
- OI assessment*

- Record FiO₂ and MAP (including type of ventilation – high frequency vs. traditional)*
- Arterial blood gas*
- Clinical laboratory assessments (See Section 3.3.2.3)
- NT-proBNP
- Randomization
- Initiation of study drug
- Assess clinical worsening
- Record concomitant medications
- Record any AEs

Some Screening and Baseline assessments may be combined (i.e., not repeated) if conducted within 3 hours of randomization (noted with “*”).

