9.2 DOCUMENTATION OF ADVERSE EVENTS

An AE or SAE occurring during the study must be documented in the subject's source documents and on the appropriate eCRF page. Information relating to the AE such as onset and cessation date and time, intensity, seriousness, relationship to study drug, and outcome is also to be documented in the eCRF (see Appendix 15.1 for definitions). Serious AEs are to be reported on the SAE Notification Form and submitted within 24 hours to United Therapeutics Global Drug Safety (Section 9.4). Where possible, AEs/SAEs should be recorded using standard medical terminology. If several signs or symptoms are clearly related to a medically-defined diagnosis or syndrome, the diagnosis or syndrome should be recorded on the eCRF page, not the individual signs and symptoms (e.g., pneumonia characterized by shortness of breath and wheezing).

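### SAP 12.2 counts adverse events that start before the first infusion on the dosing date as treatment-emergent, contrary to its own exclusion of pre-dose events

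*SAP*

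**What the plan says.** AE collection starts before treatment. Protocol 3.3.2.4: "Documentation of AEs will be recorded in the eCRF from the time informed consent is provided". There is therefore a window between consent and first dose in which AEs are recorded.

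SAP 12.2 then sorts AEs into two classes within one paragraph:

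- The first class is defined by date: "Treatment-emergent adverse events (TEAEs) are those AEs with onset date equal to or after the start date of the study drug". The sentence after it sends these events to both listings and summaries.
- Two sentences after the definition comes the complementary class, described as "the AEs occurring after signing the Informed Consent Form (ICF), but before receiving study drug". These events are to be listed but kept out of the summary tables.

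The same section puts a treatment-emergent flag on the listings. It defines the AE rate as the number of AEs divided by patient-days of exposure to study drug.

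Finer timing is collected. Protocol 9.2 has the eCRF document "onset and cessation date and time, intensity, seriousness, relationship to study drug", and the dosing listing in SAP 12.1 carries "initial dose and date and time of initial dose".

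On the pace of enrolment, Protocol 7.1 and 7.2 let some screening assessments serve as baseline if done within 3 hours of randomization. Protocol 7.2 adds: "Study drug should be initiated as soon as possible after randomization". No section gives a maximum, or a typical, time from consent to first dose.

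**The concern.** The two classes should not overlap, but they do on the dosing date. An AE that starts a few hours before the infusion, on the same date, is treatment-emergent by the date rule and non-treatment-emergent by the description of the other class. The date rule is the operational one, so a programmer who follows it puts the event into tables from which the paragraph says it should be absent.

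Safety is part of the primary objective (Protocol 2.1; SAP 2), and Protocol 10.3.3 names the incidence of treatment-emergent AEs as something to be evaluated. No inferential safety tests are planned, so the displayed counts and rates are the safety result. These infants are critically ill before dosing, and much of the trial's timing is set in hours, so a calendar-day rule is coarse. SAP Table 8-2 itself uses hour-level windows for vital signs, OI and blood gases.

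**Working it through.** The plan states no figure on this point, so there is none to reproduce. The check has three parts.

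**1. Do the two rules really overlap?** Consider an AE with onset after consent, before the first infusion, on the date of the first infusion.

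- Date rule: onset date equals start date, so the event is a TEAE and is summarized.
- Complementary class: the event precedes study drug, so it is a non-TEAE and is not summarized.

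Both apply, and the SAP has no time-based tie-break. An AE on an earlier date than the first dose is a non-TEAE under both rules, so the conflict is confined to the dosing date.

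**2. What share of pre-dose AEs falls on the dosing date?** Let T be the hours from consent to first dose (not in the documents) and d the clock time of first dose in hours after midnight. Assume d uniform on 0–24 and AE onset uniform over the T hours. The part of the pre-dose interval on the dosing date is min(d, T).

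- T ≤ 24: E[min(d, T)] = (T²/2 + T(24 − T))/24 = T − T²/48, so the share is 1 − T/48.
- T > 24: E[min(d, T)] = E[d] = 12, so the share is 12/T.

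| T (h) | Share of pre-dose AEs counted as TEAEs |
|---|---|
| 1 | 1 − 1/48 = 98% |
| 3 | 1 − 3/48 = 94% |
| 6 | 1 − 6/48 = 88% |
| 12 | 1 − 12/48 = 75% |
| 24 | 1 − 24/48 = 50% |
| 48 | 12/48 = 25% |
| 72 | 12/72 = 17% |

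Simulation agrees with the closed form. The result also depends on when infusions start:

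- Dosing only between 08:00 and 18:00: 100% at 3 h, 93% at 12 h, 54% at 24 h, 27% at 48 h.
- Dosing only between 00:00 and 06:00: 75% at 3 h, 50% at 6 h, 25% at 12 h.

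**3. What does a misplaced event do to the tables?**

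- Incidence: with 33 infants per arm (the planning figure), one infant is 1/33 = 3.0 percentage points and two are 2/33 = 6.1. This is the unit of movement, not a forecast, because the documents give no expected number of pre-dose AEs.
- AE rate: k misplaced events add k/D to a rate whose D patient-days contain none of the time in which those events arose.
- Comparison of arms: these events precede study drug under blinded 1:1 allocation, so both arms gain the same number in expectation. If a fraction q of infants in each arm has such an event, independently of later events, incidences p₁ and p₂ become 1 − (1 − p₁)(1 − q) and 1 − (1 − p₂)(1 − q). Their difference becomes (p₁ − p₂)(1 − q), a slight dilution when q is small.

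**The case against.** The case against giving this much weight is substantial.

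- **The extent is unknown.** A reader might infer from the 3-hour allowance and the prompt start of study drug that consent and dosing fall on one date, so that most pre-dose AEs are misclassified. The documents do not say so. The 3 hours limits only which screening values can double as baseline. It does not bound the time from consent to dosing, and no maximum screening period is stated. This stands: the share could be 98% or 17% across the intervals tabulated.
- **Not every table is exposed.** The causality guidance in Protocol 15.1 counts the absence of a temporal relationship, including an event that comes too early, as grounds for coding an AE not related. A pre-dose event should therefore stay out of the related-AE table. The action-taken codes in 15.1 include one for AEs before administration, which should also keep such events out of the discontinuation table. The Safety population requires a dose (SAP 6), so a pre-dose death cannot enter. This stands.
- **Many instability events go elsewhere.** Protocol 9.1.5 routes listed events that the investigator attributes to PPHN, such as hypoxia, respiratory failure and shock, to disease-related events. They are also recorded as AEs only if serious, unusual or possibly caused by study drug. This stands in part: complications of line placement, for example, are not in Table 9-1.
- **A day-level rule is defensible.** It errs toward counting events, and Protocol 15.1 defines the AE start date as a day. The description of the complementary class might also be read as the operative exclusion. This does not rescue the text. If the date rule was meant, the other description is wrong for the dosing date; if the exclusion was meant, the date rule is wrong. The paragraph must be settled either way.

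**Conclusion.** The internal conflict is real and needs no assumption: SAP 12.2 assigns pre-dose AEs on the dosing date to both classes, and its operational rule puts them in the summary tables.

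The size is not established. The share of pre-dose AEs affected rests on an undocumented consent-to-dose interval and on the uniform timing assumptions. Under those assumptions it exceeds half only when the interval is under 24 hours, which the enrolment procedures make plausible but do not fix. The number of pre-dose AEs is unknown and may be small.

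The expected consequence is modest inflation of descriptive AE counts and rates in both arms and slight dilution of any contrast. The related-AE table should be little affected. Someone might go further and infer a bias for or against Remodulin. The documents do not support that: the events arise before treatment under blinded 1:1 allocation, so no arm is favoured in expectation, although a chance imbalance of one or two infants would be visible at this sample size. The point is a correction to the safety definitions. It has no bearing on the efficacy analysis.

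**What to change.** Replace the definition in SAP 12.2 with a date-time rule. A TEAE is an AE whose onset date and time is at or after the date and time of the first study drug infusion. An AE with onset on the first-dose date and a missing onset time is treated as treatment-emergent. Apply the rule to the treatment-emergent flag and to every TEAE-based summary: the SOC and PT tables, the serious and non-serious tables, the related, severity and discontinuation tables, and the numerator of the AE rate.

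The cost is one SAP sentence and a small programming change, using times already collected. Two practical points follow. The completeness of AE onset times on the dosing date should be checked, because the missing-time rule falls back on the date comparison. The change should also be made before unblinding, so that the classification is not chosen with treatment known. The remaining limitation is that same-day events without an onset time may still be overcounted; that errs toward counting events, and the rule would then be explicit.
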